$$PE = Hi / lowPA \& E + PracticeSize + PAM + PA \& E * PAM + Casemix + \epsilon$$

$$PRO = Hi / lowPA \& E + PracticeSize + PAM + PA \& E * PAM + Casemix + \epsilon$$

$$ClinMeasures = Hi / lowPA \& E + PracticeSize + PAM + PA \& E * PAM + Casemix + \epsilon$$

We will explore differences between the two extreme PAM categories (level 1=lowest activation, 4=highest activation) in addition to examining the continuous PAM measures, as we expect the biggest differences over time differences in PRO and patient experience between patients with highest and lowest baseline PAM scores.

PRINCIPAL INVESTIGATOR (LAST, FIRST, MIDDLE): [name]

Aim 3. To assess the stability of the PA&E-outcome relationship over two measurement periods at the individual and practice-level;

Analyses addressing Aim 3. After both waves of data collection are completed, we will assess the consistency of the results at two levels- patient-level and practice-level. We will compare the regression coefficients for models at each wave to examine differences in associations of the independent variables with outcomes at each cross-section.

Aim 4. To assess changes over time (T1 vs. T2) in patient-reported outcomes of care, patient experience and clinical measures, as a function of changes over time in PA&E activities, patient activation, controlling for patient casemix.

Analyses Addressing Aim 4. We will integrate the patient survey results and the patient level results at the practice level. We will examine 'over time' effects using three approaches: 1) multilevel regression with interaction term as specified here, 2) stratified by low vs. high PA&E practices and looking at coefficient differences, 3) lagged regression (using T1 to predict T2) vs. change in T1 and T2 predicting T2), etc. The simplified equations below provide a multilevel framework for studying the impact of site PA&E activities on patient activation, patients' experiences, and patient-reported outcomes over time:

$$\Delta PRO = \Delta PA \& E + \Delta PAM + \varepsilon$$

$$\Delta PE = \Delta PA \& E + \Delta PAM + \varepsilon$$

$$\Delta ClinMeasures = \Delta PA \& E + \Delta PAM + \varepsilon$$

Given the uncertainty in distribution and variation, we will examine the inclusion of other relevant predictors including fixed effects for casemix and practice size.

Aim 5. To explore key capabilities of practice teams that might account for their greater involvement in PA&E activities to engage patients and the resulting impact on outcomes of care;

Analyses Addressing Aim 5. For these exploratory analyses, we will use a range of analytic techniques to assess the extent to which changes in team factors impact changes in PA&E activities, including multilevel regression modeling of the quantitative study data and comparative case study analyses of the multiple data sources. For example, we will triangulate the quantitative results with site visit data about the changes to PA&E activities, including treating PA&E as a continuous variable (0 to 40 on our index of activities) occurring at the practices that might explain increases or declines in the outcome measures and primary care teamwork.

$$PA \& E = Team + PracticeSize + Casemix + \varepsilon$$

We will explore an overall teamwork composite, but will also examine differences in effect sizes using the various team subscales assessed in the survey (e.g., relational coordination, team participation, team culture).

Aim 6. To explore the team feedback process to assess the extent to which feedback was used and could explain changes in team-related influences over time.

Analyses Addressing Aim 6. We will use comparative case analyses to compare data feedback processes and teamwork factors at the 16 practices as they relate to improvements in PROs and patient experience over time^{81, 82}.

PRINCIPAL INVESTIGATOR (LAST, FIRST, MIDDLE): [name]

CRITERION 3 – TECHNICAL MERIT (Also see Research Plan and Analysis Plan under Section C. Study Design or Approach.)

D. Project Milestones

Table 3. Project Milestones and Timeline

0-6 months	7-12 months	13-18 months	19-24 months	25-30 months	31-36 months
Wave 1 PA&E Survey Finalize enrollment of practice sites	Site feedback on wave 1 PA&E survey		Wave 2 PA&E Survey	Site feedback on wave 2 PA&E survey	
Patient identification and selection	Wave 1 Patient survey: - Patient Activation Measure (PAM) - Patient-reported outcomes (PROMIS) - Patient experience Retrospective clinical measures from EHR (BP, etc.)	Feedback results of wave 1 Patient Survey and clinical measures to practices	Wave 2 Patient survey: - Patient Activation Measure (PAM) - Patient-reported outcomes (PROMIS) - Patient experience Retrospective clinical measures from EHR (BP, etc.)	Feedback results of wave 2 Patient Survey and clinical measures to practices	
Completion of teamwork assessment instruments	Feedback to practices results of teamwork assessments	Completion of teamwork assessment instruments	Feedback to practices results of teamwork assessments	Feedback overall results to the ACO practices	
Site Visit #1			Site Visit #2		
Formation of patient Advisory Groups	Feedback of teamwork assessment to patient advisory groups	Feedback of patient survey and clinical data to patient advisory groups	Feedback of teamwork assessment to patient advisory groups	Feedback of patient survey and clinical data to patient advisory groups	
	Project deliverables on results to date	-Integration of baseline patient sources (patient survey and clinical data) and practice data sources (PA&E and teamwork results) Analysis of Wave 1 data	Project deliverables on results as of 24 months	Integration of baseline patient sources (patient survey and clinical data) and practice data sources (PA&E and teamwork results) Analysis of Wave 2 data and over time changes, report writing, and development of papers for publication etc.	

E. Patient Population

DIVERSE STUDY POPULATION

As described in Table 2 above, both HCP and Advocate ACOs serve a diverse patient population. HCP's patient population includes 55% Latino, 15% Asian/Pacific Islander, 10% African American, and 25% non-Latino white patients. Between its Medicare Shared Savings and commercial ACOs, its payer mix is 18.5% Medicare, 13% Medicaid, and 68% commercial. Advocate's large patient population includes 22% African American, 8% Latino, 3% Asian, as well as 1% each American Indian/Alaska Native, Middle East, and Eastern Indian. Its payer mix is 70% commercial, 25% Medicare, and 4% employee. Thus the proposal provides an opportunity to examine the extent to which PA&E activities may need to be customized to meet the needs of diverse populations.

PRINCIPAL INVESTIGATOR (LAST, FIRST, MIDDLE): [name]

F. Research Team and Environment

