We will randomly select 273 patients with diabetes and/or CVD from each of the 16 practices. Given the 16 practice sites, we will have data from 4,368 patients. We will follow them as cohorts over a two-year period. See Figure 2 below for selection design. Patients will complete the 13-item PAM measure, patient-reported outcomes (PROMIS), and experience of care measures between 7-12 months and again between 19-24 months. We will obtain measures of blood pressure, HbA1c and LDL-C at 12 months and 24 months from the EHR. We expect a 50% response rate to the first survey round and 65% response rate to the second survey round, with 3% undeliverable and 20% attrition over the two-measurement period, leaving 1102 patients, or 69 patients per practice, available for analysis. The calculations provided

PRINCIPAL INVESTIGATOR (LAST, FIRST, MIDDLE): [name]

below for the PROMIS self-reported measures and for blood pressure provide evidence of sufficient statistical power to detect meaningful differences between practices on these key variables of interest.

Figure 2. Selection and engagement of ACO practices, patients, and teams

Study Sites

Advocate Health Care (Advocate) and Advocate Physician Partners (APP) operate both a commercial and a Medicare ACO. In 2011, Advocate joined with its largest commercial insurance partner to create AdvocateCare, providing care to 370,000 covered lives. In 2012, Advocate was chosen to participate in the Medicare Shared Savings Program (MSSP), becoming one of the largest Medicare ACOs in the country, serving an estimated 106,000 Medicare beneficiaries.

HealthCare Partners ACO (HCP) was formed in 2010 as one of the early Dartmouth-Brookings demonstration ACOs⁴⁶. They hold both CMS and private payer risk-based contracts collectively accountable for 50,000 lives. They serve high proportions of Medicaid patients in low-income communities who tend to face many social and financial barriers to self-management in care for diabetes and CVD. Approximately 55% of HCP's Southern California patients are Latino. Table 2 compares key characteristics of the partnering ACOs. Both Advocate and HCP are highly committed to this study as indicated by their letters of support and related materials in this proposal.

Table 2. Summary of key characteristics of the two participating ACOs

	Advocate ACO	HealthCare Partners ACO

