To project the sample size requirements given 16 practices (8 high PA&E and 8 low PA&E), we estimated the design effect (DE) to account for the clustering of patients within practice sites. While PROMIS data from participating ACO patients are presently unavailable, recent studies of change over time on the PROMIS physical functioning measure informed our sample size estimates for the PROMIS measure⁴⁷. Having been selected using item-response theory (IRT) methods and extensive testing, the PROMIS physical functioning measure is a precise measure that is sensitive to small changes in physical functioning over time. Given the published estimates and a range of design effect estimates (intraclass correlation (ICC)=0.01-0.04) to account for the clustering of patients within practices, a clinically meaningful change (e.g.,

PRINCIPAL INVESTIGATOR (LAST, FIRST, MIDDLE): [name]

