a 3-5 point change out of 100) on the PROMIS physical functioning measure can be detected with 50-65 patients per practice. Based on prior experience, we expect a minimum 50% response rate for completing the first patient survey and a 65% response rate for the second survey. We expect a 3% rate for undeliverable addresses and a 20% drop-out rate between the two survey periods based on our previous research. Patient-level blood pressure data from adult diabetic patients at HCP ACO practices were used to calculate the design effect (ICC=0.01-0.02). Previous research suggests that population-level improvements in blood pressure on the order of 3-5 mm Hg are clinically meaningful⁴⁸⁻⁵⁰. Based on a two-sided difference of means with a power of 0.90, we estimate that an average of 140 patients per practice are needed to detect a 3 mm Hg difference in change in systolic blood pressure over time between the high (n=8) vs. low (n=8) PA&E practices. Based on these calculations, we will randomly select 273 patients per practice (n=4,368) with diabetes or CVD diagnoses from each of the practice sites and teams in the two ACOs for inclusion in the study. Given the assumptions of response rates and attrition noted above, this will yield a final total of 1102 patients with two time points for analysis of the PROMIS (69 patients per site). In addition we expect to receive retrospective clinical outcomes data from the EHR for most of the sampled patients (n=4,368). Thus, even with slightly lower than expected survey response rates, our study will be sufficiently powered to detect clinically meaningful differences between high and low PA&E practices on both patient-reported (PROMIS) and clinical, e.g., blood pressure, outcome measures.

MEASURES

Measurement of Site PA&E Activities

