Quantum Market Research, a survey firm in Oakland, CA, will be hired to administer the patient survey. Given the published estimates and a range of design effect estimates (intraclass correlation (ICC)=0.01-0.04) to account for the clustering of patients within practices, a clinically meaningful change (a 3-5 point change out of 100) on the PROMIS physical functioning measure can be detected with 50-65 patients per practice. Based on prior experience, we expect a minimum 50% response rate for completing the first patient survey and a 65% response rate for the second survey. We

PRINCIPAL INVESTIGATOR (LAST, FIRST, MIDDLE): [name]

expect a 3% undeliverable addresses and a 20% drop out rate between the two survey periods based on our previous research. Patient-level blood pressure data from adult diabetic patients at HealthCare Partners practices were used to calculate the design effect (ICC=0.01-0.02). Previous research suggests that population-level improvements in blood pressure on the order of 3-5mm Hg are clinically meaningful.^{48, 49} Based on a two-sided difference of means with a power of 0.90, we estimate that an average of 140 patients per practice are needed to detect a 3 mm Hg difference in change in systolic blood pressure over time between the high (n=8) vs. low (n=8) PA&E practices. Based on these calculations, we will randomly select 273 patients per practice (n=4,368) with diabetes or CVD diagnoses from each of the practice sites and teams in the two ACOs for inclusion in the study. Given the assumptions of response rates and attrition noted above, this will yield a final total of 1102 patients with two time points for analysis of the PROMIS (69 patients per site). In addition we expect to receive retrospective clinical outcomes data for all sampled patients (n=4,368) from the electronic health record. Thus, even with slightly lower than expected survey response rates, our study will be sufficiently powered to detect clinically meaningful differences between high and low PA&E practices on both patient-reported (PROMIS) and clinical, e.g., blood pressure, outcome measures.

Two site visits to each of the two ACOs will be conducted at two points in time to gain an insight to the strategic goals of the ACOs in improving patient activation and engagement and fostering high functioning interdisciplinary primary care teams: (1) during the 0-6 month start-up phase of the study, and again (2) during the period of 18-24 months.

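### The change analyses for PROMIS and patient experience (Aims 2 and 4) rest on about half of the expected wave-1 respondents, with no planned correction for nonresponse at either wave

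*Combined protocol and SAP*

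**What the plan says.** The Patient Selection section plans that "we will randomly select 273 patients per practice (n=4,368) with diabetes or CVD diagnoses", in the setting "given 16 practices (8 high PA&E and 8 low PA&E" practices. On survey yield it states that "we expect a minimum 50% response rate for completing the first patient survey and a 65% response rate for the second survey", and adds: "We expect a 3% rate for undeliverable addresses and a 20% drop-out rate between the two survey periods". The result is that "this will yield a final total of 1102 patients with two time points for analysis of the PROMIS (69 patients per site"). The Research Plan gives the same figure as "leaving 1102 patients, or 69 patients per practice, available for analysis".

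In the Analysis Section, Aims 1 and 3 are analysed separately at each wave. The text for Aim 2 models change in the patient-reported outcomes with practice random effects. The Aim 4 equations put change in PRO and in patient experience on the left and change in PA&E and in PAM on the right.

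On data beyond the survey, the Berkeley human-subjects section says "we expect to receive retrospective clinical outcomes data for all sampled patients (n=4,368) from the electronic health record". The corresponding sentence under Patient Selection expects EHR data for most sampled patients, not all. Age and sex come from ACO records (Patient Demographics), and the ACOs link EHR data to the study ID (Sources of Materials). The text available for review mentions no nonresponse weights, no imputation, no model that keeps patients with one survey, and no comparison of responders with non-responders.

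**The concern.** A change score needs both surveys. Followed literally, the Aim 2 and Aim 4 analyses of PROMIS and patient experience are completer analyses on a quarter of the sample. The casemix terms (age, sex, education, comorbidity) adjust only among those who answered.

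The study's own logic makes selection plausible. The Research Plan posits that high-PA&E practices activate patients more effectively, and the PAM section links activation to positive health behaviours and better emotional health. Returning two surveys about one's own care may well be such a behaviour. The exposure could then influence who responds, and how strongly response depends on health, differently in the two groups. That would bias the high-versus-low contrast, and the completers alone could not reveal it.

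**Working it through.** **1. The plan's own figure.** Inputs are from Patient Selection: 273 per practice, 16 practices, 3% undeliverable, 50% first response, 20% drop-out, 65% second response.

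- Sampled: 273 × 16 = 4,368.
- Wave-1 respondents: 4,368 × 0.97 × 0.50 = 2,118 (132 per practice).
- Both waves: 2,118 × 0.80 × 0.65 = 1,102 (69 per practice). The plan's figure reproduces.

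**2. The two losses.**

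- No wave-1 score: 4,368 − 2,118 = about 2,250 (51.5% of the sample).
- Wave 1 but not wave 2: 2,118 − 1,102 = about 1,016 (48% of wave-1 respondents).
- Both waves: 1,102/4,368 = 25.2% of the sample and 1,102/2,118 = 52% of wave-1 respondents.

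**3. Precision gained by keeping one-wave respondents.** Let ρ be the correlation between waves; it is not in the documents, and 0.5-0.8 is assumed. Let r = 0.52. The patient-level variance of mean change, relative to completers only, is [(1+ρ) + r(1−ρ)]/2.

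- ρ = 0.5: (1.5 + 0.26)/2 = 0.88.
- ρ = 0.8: (1.8 + 0.104)/2 = 0.952.

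The plan gives "a range of design effect estimates (intraclass correlation (ICC)=0.01-0.04"); I apply that range to change. With 69 patients per practice, the total variance ratio is [ratio × (1−ICC)/69 + ICC] / [(1−ICC)/69 + ICC].

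- ICC 0.01, ρ = 0.5: 0.02263/0.02435 = 0.929; SE ratio 0.964.
- ICC 0.04, ρ = 0.8: 0.05325/0.05391 = 0.988; SE ratio 0.994.

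The SE therefore falls by about 1-4%, before any variance added by weights.

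**4. Illustrative bias in an outcome level.** Take a standard normal outcome Y and logit P(complete) = a + bY, with a set to give the completion rate. All slopes and group-specific rates are assumptions.

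- Completion 25%: E[Y | complete] = 0.075 for b = 0.1 and 0.221 for b = 0.3; difference 0.146 SD.
- Rates varied between 22.5% and 27.5%: difference 0.136-0.157 SD.
- Equal slopes of 0.3 with rates of 22.5% and 27.5%: 0.229 − 0.214 = 0.015 SD.

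**5. Illustrative bias in change.** If completion depends on the wave-1 score, the bias in mean change is (1−ρ) times the difference in the wave-1 mean of completers.

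- Overall completion of 25%: 0.146 × 0.5 = 0.073 SD (ρ = 0.5); 0.146 × 0.2 = 0.029 SD (ρ = 0.8).
- Loss between waves only, 52% retained: 0.141 − 0.048 = 0.093; × 0.5 = 0.046 SD; × 0.2 = 0.019 SD.

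The range is about 0.02-0.07 SD. It touches 0.08 SD if the group with the weaker slope completes at 27.5% and the other at 22.5%. The PROMIS section puts the minimally important difference at about 0.20 SD.

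**6. Simulation check.** The simulation used 16 practices, 132 wave-1 respondents each, about half lost, SD 10, and loss depending on wave-1 PROMIS in opposite directions in the two groups, which is deliberately strong. Completers-only bias was 1.4 points (ρ = 0.5) and 0.9 points (ρ = 0.7). It was about zero when all wave-1 respondents were used. When loss did not depend on wave-1 PROMIS, neither analysis was biased.

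**The case against.** The 1,102 is a forecast of yield in a sample-size section. No sentence excludes patients with one survey. Aim 1, the central question, and Aim 3 are analysed by wave and can use every respondent at that wave. Aim 2 already names a multilevel model. Aim 4 lists several approaches, and its lagged option conditions on the wave-1 score, which would largely remove the mechanism in step 5. This stands: the completer restriction is inferred from the stated set and the change equations, and it applies to Aims 2 and 4 only. It does not remove the point, because the change equations cannot be fitted without both waves and nothing is said about nonresponse.

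A reader might infer four stronger things that the documents do not support.

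- *The study throws away three quarters of its patients, and a mixed model would recover them.* Most of that loss is the 2,250 without a wave-1 score. A model fitted to respondents recovers nothing from them.
- *A fuller analysis would be clearly more precise.* The gain is 1-4% in SE, and weighting may cancel it.
- *Bias in change comes close to the minimally important difference.* The figure of about 0.15 SD is for a level, and it needs slopes that differ threefold between groups, for which the documents give no basis.
- *EHR data are held on everyone.* One section says all and the other says most. In addition, the HbA1c control measure is defined for patients with diabetes, so values may be absent for patients with CVD only.

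**Conclusion.** The point holds in this limited form and is worth fixing. As written, the PROMIS and patient-experience change analyses use about 52% of expected wave-1 respondents. The by-wave analyses face nonresponse of about half the sample. Neither has a planned correction, although the study's own hypothesis gives a reason for response to differ by PA&E group.

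The size is uncertain. Under the assumed unequal slopes, bias is 0.14-0.16 SD for a level and 0.02-0.07 SD for change (ρ 0.5-0.8); with equal slopes it is negligible. The change figure also assumes that response depends on the wave-1 score. If it depends on the wave-2 score or on unrecorded factors, bias could be larger and the correction below would not remove it. The case for acting is bias control and a visible sensitivity analysis, at low cost.

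**What to change.** Prespecify the following.

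1. For Aim 2 and the high-versus-low contrast over time, fit a two-wave mixed model with practice and patient random effects that keeps all wave-1 respondents. Baseline PAM is collected at wave 1, so the interaction can be fitted in this set. Aim 4 models with change in PAM still need both waves; say so.
2. For the by-wave and change analyses, weight by the inverse probability of response at the relevant wave. Estimate it from age, sex, diagnosis, practice and available EHR measures (blood pressure, LDL-C, and HbA1c where applicable) in sampled patients with EHR data.
3. Compare responders with non-responders on those variables, by PA&E group and wave.
4. Report the unweighted completer result as a sensitivity analysis.
5. Reconcile the two statements on EHR coverage (most versus all), since this determines who can enter the response model.

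The cost is analyst time; no new data collection is needed. The weights will add some variance, missing EHR values need their own stated handling, and the correction works only to the extent that recorded data explain nonresponse.

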we define each of these concepts, their specific measures, and the role they play in our overall logic model and research design. The definition of *patient activation* used throughout the proposal is the patient's understanding of their role in the care process and having the knowledge, skills, and confidence to take on that role. *Patient engagement* denotes a broader concept, which includes patient activation, the interventions designed to increase it, and the patient behaviors that result from it.

CRITERION 1 – IMPACT OF THE CONDITION

We will study patients with diabetes (ICD-9CM 250.XX) and/or CVD (ICD-9CM 393-459). Uncontrolled diabetes can result in high-cost complications including retinopathy¹¹, incident myocardial infarction (MI), stroke, congestive heart failure (CHF), and nontraumatic lower extremity amputation (LEA)¹², contributing to high health care expenditures in the United States¹³. These and related chronic conditions represent an estimated 75 percent of all U.S. health care expenditures¹⁴.

It is estimated that 26% of adults over age 18 have multiple chronic conditions (MCC) and this percent has increased since 2001. The prevalence of MCC significantly increases with age¹⁵. For adults over 65, as many as 85 percent suffer from one or more chronic diseases¹⁶. At least 18.8 million Americans have diagnosed diabetes. An additional 7 million people are estimated to be undiagnosed¹⁷. Diabetes is the sixth leading cause of death and is rising as a cause of mortality as well as in prevalence, with an annual total cost of \$245 billion for diagnosed cases¹⁸. Heart disease (which includes CAD and CHF among other conditions) affects about 26.5 million in the US while hypertension affects over 76 million Americans¹⁹. The cumulative death toll from CVD was nearly 600,000 deaths per year in 2010²⁰, with 715,000 heart attacks per year in the U.S.²¹ at an annual cost of \$108.9 billion for health care services, medications, and lost productivity²². Altogether, CVD accounts for 29 percent of all deaths in the U.S. No other group of chronic conditions imposes this level of impact on our population; however many people are still undiagnosed or untreated. Among those diagnosed and treated, levels of adherence to medication and lifestyle changes remain low and physicians often do not know how to better activate patients in clinical settings.

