Why Selected?	
 Named among the nation's Top 5 largest health systems based on quality by Truven Analytics, Largest health system in Illinois and one of the largest health care providers in the Midwest. Operates more than 250 sites of care, including more than 150 primary care sites and 12 hospitals that encompass 11 acute care hospitals, the state's largest integrated children's network, five Level I trauma centers (the state's highest designation in trauma care), two Level II trauma centers, one of the area's largest home health care companies, and one of the region's largest medical groups. Advocate Health Care trains more primary care physicians and residents at its four teaching hospitals than any other health system in the state 	
 Large, well-developed, well-established integrated delivery system with group and IPA models representative of American health care (69 primary care sites). 30+ yrs of integrated care and health delivery experience and refinement: directly/indirectly aligns with IHA's Triple Aims. Diverse patient populations with wide arrays of cultural/socioeconomic backgrounds and varying ranges of health status. Innovative use of patient-centric health /wellness programs coupled with technology. Robust data warehouse. Broad dissemination of best practices nationally. 	HEALTH CARE TEAM SELECTION We define the membership of primary care teams based on administrative designations of team membership. Based on our preliminary data, we expect a varying number of care teams up to a total of approximately 160 teams from the 16 practice sites. Within each of the practices, we will randomly select

patients from teams with sufficient patients with diabetes and/or CVD diagnoses to equal the 273 patients with diabetes and/or CVD diagnoses. While the statistical analysis will be at the practice level, we will provide team-level scores to the practices for their use.

PATIENT SELECTION

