Patient Reported Outcome Measure – PACIC-11

The Patient Assessment of Chronic Illness Care scale (PACIC-11) developed and validated by Glasgow et al⁵⁸ (Medical Care, 2005; see Appendix II) will be used to assess the extent to which practices engaging in more PA&E activities and with higher team functioning will be able to effectively improve patients' experiences of chronic illness care over time. The PACIC-11 has high Cronbach's alpha internal consistency, reliability of 0.93, and reasonable test-retest reliability of 0.58. It also demonstrates convergent validity with the Hibbard PAM measure and several dimensions of the Ambulatory Care Experiences Survey (ACES), the precursor to the Clinician Group Consumer Assessment of Healthcare Providers and Systems (CG-CAHPS) survey ([name] and Crane 2011)⁵⁹. We will supplement the PACIC-11 with selected items from the Ambulatory Care Experiences Survey (ACES) focused on patients' experiences of primary care teams ([name], Rogers et al., 2007)⁶⁰. (See Appendix II)

Clinical Measures

Based on each site's EHR, we will have de-identified data for blood pressure, lipids, and HbA1c to measure percentage of hypertensive patients with blood pressure controlled (<140/90 mm Hg), percentage of patients with diabetes with blood sugar controlled (HbA1c <8.0%), and percentage of patients with cardiovascular conditions or diabetes whose lipids are controlled (LDL-C <100 mg/dL). The patient survey sampling frame includes "established" patients of each primary care physician and team. The adult diabetic and CVD patients will need to have at least two primary care visits in the baseline year (2013) to improve the reliability of reports of patients' experiences of care and to focus on an established patient population that has a high propensity to maintain clinical relationships and receive routine primary care over time. Since attribution of patients to practices and PCPs is a contentious issue in performance measurement in improvement^{61, 62}, restricting the sample to patients with diabetes and/or CVD who have ongoing relationships will also aid in team acceptance of the feedback data.

Patient Demographics

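### The figure n=4,368 is not the analysis denominator for HbA1c, and the claim of adequate power for clinical outcomes rests on a single blood-pressure calculation

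*Combined protocol and SAP*

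**What the plan says.** Section C (Patient Selection) derives one clinical sample size: 140 patients per practice, two-sided, power 0.90, for a 3 mm Hg difference in change in systolic blood pressure between 8 high and 8 low PA&E practices, with ICC 0.01-0.02. It then says "we will randomly select 273 patients per practice (n=4,368) with diabetes or CVD diagnoses". The Health Care Team Selection text describes the draw as "patients from teams with sufficient patients with diabetes and/or CVD diagnoses to equal the 273 patients with diabetes and/or CVD diagnoses". Neither gives a diabetes stratum, a minimum or an expected share.

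On data volume, Patient Selection says "In addition we expect to receive retrospective clinical outcomes data from the EHR for most of the sampled patients (n=4,368". The Berkeley human-subjects section is stronger: "we expect to receive retrospective clinical outcomes data for all sampled patients (n=4,368) from the electronic health record". Both conclude that the study is sufficiently "powered to detect clinically meaningful differences between high and low PA&E practices on both patient-reported (PROMIS) and clinical, e.g., blood pressure, outcome measures".

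The Clinical Measures section sets narrower denominators. HbA1c is the "percentage of patients with diabetes with blood sugar controlled (HbA1c <8.0" percent). Blood pressure control is defined for hypertensive patients, and LDL-C control for patients with cardiovascular conditions or diabetes. Eligibility is wide: "We will study patients with diabetes (ICD-9CM 250.XX) and/or CVD (ICD-9CM 393-459").

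In the Analysis Section, the clinical-measure equations for Aims 1 and 2 include PAM as a covariate. PAM comes from the patient survey.

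**The concern.** HbA1c is one of three clinical measures in the study's central question, yet no effect size, SD, ICC or sample size is given for it. The power statement covers clinical outcomes in general and names blood pressure only as an example, so a reader will take it, and the 4,368 beside it, to cover HbA1c too.

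Two restrictions lie between 4,368 and the patients in an HbA1c model: the diabetes restriction and, because PAM is a covariate, the survey-response restriction. The second also applies to blood pressure. If neither is counted, a wide confidence interval for glycaemic control could be reported from a study described as adequately sized for it.

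**Working it through.** **1. The plan's own figures.** 16 x 273 = 4,368. Also 4,368 x 0.97 x 0.50 x 0.65 x 0.80 = 1,101.6, or 68.9 per practice. These match the printed 4,368, 1,102 and 69. The 140 cannot be reproduced, because the SD of change and alpha are not stated. At an assumed two-sided alpha of 0.05 it implies an SD of about 14.2 mm Hg (ICC 0.01) or 11.3 (ICC 0.02). Those values are not implausible, so the 140 itself is not shown to be wrong.

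**2. Denominators per practice.** Let s be the diabetes share of the sampled patients, which the plan does not give.
- EHR only, no PAM: 273 x s. This reaches 140 when s = 140/273 = 51.3%.
- With wave-1 PAM: 273 x 0.97 x 0.50 x s = 132.4 x s. Even s = 100% gives 132, below 140.
- This takes the models as complete-case, since no imputation of PAM for non-respondents is described.

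**3. What the documents suggest about s.** The only figures are national, in Criterion 1: 18.8 million with diagnosed diabetes, and heart disease that "affects about 26.5 million in the US while hypertension affects over 76 million Americans".
- If hypertension counts as CVD: from 18.8/(18.8 + 26.5 + 76) = 15.5% (no overlap) to 18.8/76 = 24.7% (full overlap), or about 42 to 68 per practice.
- If only heart disease counts: from 18.8/(18.8 + 26.5) = 41.5% (no overlap) to 18.8/26.5 = 70.9% (full overlap), or about 113 to 194 per practice.

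**4. Power.** Effective n per arm is 8m/(1 + (m - 1) x ICC). At m = 140 this is 468.6 (ICC 0.01) or 296.3 (ICC 0.02). Fixing the standardised effect that gives 0.90 power at m = 140, power at m is Phi(3.2415 x sqrt(neff(m)/neff(140)) - 1.96).

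Worked example, s = 25%, no PAM, ICC 0.01: m = 68.25; neff = 546/1.6725 = 326.5; sqrt(326.5/468.6) = 0.835; 3.2415 x 0.835 - 1.96 = 0.746; power 0.77.

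| Diabetes share (assumed) | No PAM: m | Power, ICC 0.01 / 0.02 | With PAM: m | Power, ICC 0.01 / 0.02 |
|---|---|---|---|---|
| 25% | 68 | 0.77 / 0.82 | 33 | 0.56 / 0.67 |
| 40% | 109 | 0.87 / 0.88 | 53 | 0.71 / 0.78 |
| 50% | 136 | 0.90 / 0.90 | 66 | 0.77 / 0.82 |
| 100% | 273 | 0.95 / 0.93 | 132 | 0.89 / 0.90 |

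**5. On the scale of the HbA1c outcome.** It is a percentage controlled, not a mean. For an assumed control rate of 50-70% and ICC 0.01-0.02, the difference detectable with 0.90 power is about 9-13 percentage points at m = 140 and about 11-15 at m = 68.

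**6. Blood pressure.** Taking the national figures with no overlap, the hypertensive share is 76/121.3 = 63%. Without PAM that is 171 per practice, above 140. With PAM it is 0.63 x 132 = 83. Since 132 is already below 140, no hypertensive share reaches 140 in the PAM-adjusted model.

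**The case against.** A reader might infer that HbA1c is bound to fall well short of 140. The documents do not support that for the EHR-only denominator. The national figures point to a shortfall if hypertension counts as CVD, which the broad code range makes a natural reading, but the heart-disease-only reading straddles 140. They are also population counts, not the frame of established patients with at least two primary care visits, and the diabetes count leaves out a further 7 million undiagnosed.

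Nor is 140 a requirement for HbA1c. It was derived for mean systolic change, so missing it does not by itself show that a binary HbA1c comparison is underpowered. Clustering also limits the loss: halving the patients from 140 to 68 costs 8 to 13 points of power, not half of it.

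The plan never says that HbA1c values will exist for all 4,368. Patient Selection says most of the sampled patients and gives blood pressure as its example, and Clinical Measures states each denominator openly.

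Finally, the ACO data-transfer text in the human-subjects section and under Consortium Contractual Arrangements describes the clinical extract by diagnosis and visit count, with no 273 limit. If it covers all eligible patients, the draw does not cap HbA1c in a model without PAM. The sample-size text, however, ties the clinical n to sampled patients, so this is unresolved.

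All of this stands as a limit on the size of the problem. It does not supply an HbA1c calculation, and the transfer argument does not help a model with PAM, which only survey respondents can provide.

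**Conclusion.** The point holds as a mismatch between a stated size and the planned analysis. The 4,368 is not the HbA1c denominator, and the general claim of adequate clinical power has no HbA1c sizing behind it. In the PAM-adjusted models, HbA1c is below 140 per practice at any diabetes share, though only slightly if nearly every sampled patient had diabetes. Without PAM, a shortfall is plausible but not established.

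At an assumed 25% share, power is about 0.77-0.82 without PAM and 0.56-0.67 with it. These values assume two-sided 5%, the blood-pressure standardised effect and ICC carried over to HbA1c, the plan's response rates, and no missing laboratory values.

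It would also be wrong to infer that blood pressure is safe: its PAM-adjusted model starts from the same 132, and the calculation concerns mean change while the outcome is percentage controlled. Nor do the documents support a fixed quota of 140 patients with diabetes. Under the plan's response rates it would leave 140 x 0.97 x 0.50 = 68 per practice in the PAM-adjusted model.

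**What to change.** - In Patient Selection and the matching Berkeley human-subjects text, replace n=4,368 for clinical outcomes with the expected denominator per measure: diabetes for HbA1c, hypertensive for blood pressure, CVD or diabetes for LDL-C. Show each with and without the PAM restriction, and reconcile the two statements of how many sampled patients will have EHR data.
- Give the detectable difference for each control percentage over a stated range of diabetes shares and ICCs.
- Withdraw the statement of sufficient power for HbA1c, and for blood pressure in the PAM-adjusted model, unless those figures support it.
- State whether the EHR extract covers only the 273 sampled patients per practice or all eligible patients.

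These are changes of text and calculation only. They need no extra patients; the cost is a less favourable stated n. Stratifying the within-practice draw by diagnosis is an option to consider before sampling. The ACOs already select on diagnosis, but it would mean fewer CVD-only patients and some loss of precision from weighting in the whole-sample outcomes, and it would not remove the PAM restriction.
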